3.3. Analysis Periods and Analysis Time Points

3.3.1. Relative Day

The timing of an assessment or an event relative to a reference date will be calculated as follows:

When the concerned date is before the reference date:

$$\text{Relative day (days)} = \text{concerned date} - \text{reference date}$$

When the concerned date is the equal or later than the reference date:

$$\text{Relative day (days)} = \text{concerned date} - \text{reference date} + 1 \text{ day}$$

Where:

- The *concerned date* could be the measurement date of the assessment, or the start, or end date of the event.
- The *reference date* default is the date of the first dose of study drug administration, unless specified otherwise.
- *Date* implies a complete date having day, month, and year available. Unless otherwise specified, the *relative day* will remain missing when it cannot be calculated due to absence or incompleteness of the concerned and/or reference dates.

The general terms of this formula also apply when similar relative timings are required in other time units, for example in minutes.

3.3.2. Analysis Periods

All event-type data (e.g. adverse events) and assessments will be allocated to analysis periods according to [Table 1](#).

Table 1 Analysis Periods

Analysis Period	Start Analysis Period	End Analysis Period
Screening	Date of signing the ICF	Date of first study drug administration - 1 day
Treatment	Date of first study drug administration	Date of last study drug administration + 30 days
Follow-up [#]	End date of the preceding analysis period + 1 day	Date of last contact

ICF: informed consent form

[#] If the last study drug administration plus 30 days is after date of last contact, the study will not include a follow-up period. The last analysis period will end on the date of last contact.

If times are collected or other information with respect to timing (e.g. before or IMP intake) this information will be taken into account in addition to the dates. The last analysis period will always end on the date of last contact.

3.3.3. Analysis Windows

All assessments, including data collected on unscheduled visits, will be allocated to analysis windows based on the relative day of the assessment (see Section 3.3.1) and according to the algorithm in Table 2. TLFs will present the analysis windows.

Table 2 Analysis Windows for All Endpoints:

Time point label	Target day	Interval lower bound	Interval upper bound
Baseline	1	-INF	1
Week 2	15	2	22
Week 4	29	23	43
Week 8	57	44	71
Week 12	85	72	99
Week 16	113	100	127
Week 20	141	128	162
Week 26	183	163	197
Week 30	211	198	+INF

INF=infinity

Addendum: alternative approach due to COVID-19 pandemic

The Urgent Safety Measures (USMs dated 02-April-2020) described in CSP Amendment 2 allow to enlarge the visit window at the end of the treatment period (Visit 9, Week 26; from -28 days up to +56 days) including extension of study medication intake, i.e. up to a maximum of 56 days beyond 26 weeks of treatment. Hence, for patients having to extend treatment due to COVID-19, this could potentially result in end-of-treatment assessments being allocated to the FU/W30 analysis window and thus having missing data for the primary analysis time point W26. To assess the impact of this ‘missing’ data on the efficacy results, sensitivity analyses will be included in which these specific assessments are assigned to W26.

Definition of Baseline

For all endpoints, except ECG parameters and spirometry, baseline is defined as the last non-missing value before the first study drug administration. If multiple values qualify as last value, the mean of these values will be used in the analysis.

For spirometry endpoints, the mean of the analysis values (detailed in Section 5.2.2 for spirometry) before the first dose of study medication (including screening, baseline and unscheduled values as applicable) will be used to define the baseline value to reduce variability.

For electrocardiogram (ECG), the baseline is defined as the mean of the last recorded triplicate before the first study drug administration. If no triplicate is available before the first dose of study medication intake, the mean of the last duplicate ECG will be used, otherwise, the last ECG value will be considered as baseline.

Selection of Visits

Per parameter and analysis window, the value closest to the target date will be used in analysis tables and figures. Other values will be listed only. If more than one value is located at the same distance from the target day, then the latest in time will be selected. If, after the previous selection, multiple values still qualify, the mean of these values will be used in the analysis.

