6.10. SCHEDULE OF ACTIVITIES

For detailed instructions on the clinical study procedures, please see referred Sections and Section 6.1, “Timing of Assessments”.

EVENT	SCR	TREATMENT PERIOD									FU
		2	3	4	5	6	7	8	9	EOT	
Study visit	1 ¹	2	3	4	5	6	7	8	9	EOT	10/ EOS
Study week (W) or day (D) ± days (d)	D-28 to D-1	D1	W2 ±2d	W4 ±2d	W8 ±4d	W12 ±4d	W16 ±4d	W20 ±4d	W26 ⁶ ±6d		W30 ⁷ ±4d
Informed consent (Section 6.3 and Section 10.4.2)	✓										
Dispense subject participation card (Section 10.2.4)	✓										
Send HRCT (historical or new ²) for central review (Section 6.3)	✓										
Send LB (if available) for central review (Section 6.3)	✓										
Demographics (Section 6.3)	✓										
Medical history/concurrent illnesses (Section 6.3)	✓										
Alcohol consumption and smoking habits (Section 6.3)	✓										
Inclusion/exclusion criteria (Section 6.3)	✓	✓									
Physical examination (Section 6.5.3)	✓ ³	✓	✓	✓		✓		✓	✓ ³	✓ ³	✓ ³
12-Lead ECG (Section 6.5.4)	✓	✓	✓			✓		✓	✓	✓	✓
Vital signs (Section 6.5.5)	✓	✓	✓	✓	✓	✓	✓	✓	✓	✓	✓

¹ Screening assessments need to be performed within 28 days before Day 1 and may be split into multiple days or visits.

² If there is no historical HRCT available, a new HRCT needs to be planned and performed. Only if for logistic reasons it is not possible to perform a new HRCT within the planned screening period and after approval of the medical monitor it is allowed to extend the screening period with maximum 2 weeks.

³ At screening include height and weight; at Visit 9/EOT and Visit 10/EOS include weight.

EVENT	SCR	TREATMENT PERIOD									FU
		2	3	4	5	6	7	8	9	EOT	
Study visit	1 ¹										
Study week (W) or day (D) ± days (d)	D-28 to D-1	D1	W2 ±2d	W4 ±2d	W8 ±4d	W12 ±4d	W16 ±4d	W20 ±4d	W26 ⁶ ±6d		W30 ⁷ ±4d
Spirometry (Section 6.4.1)	✓ ⁴	✓ ⁴		✓	✓	✓	✓	✓	✓ ⁴	✓	✓
SGRQ (Section 6.4.2)		✓				✓			✓	✓	
Clinical laboratory tests (hematology, coagulation, clinical chemistry, urinalysis) (Section 6.5.2)	✓	✓	✓	✓	✓	✓	✓	✓	✓	✓	✓
Serology (Section 6.5.2)	✓										
FSH test (Section 6.5.2)	✓										
Pregnancy test (Section 6.5.2)	✓										
PK blood samples (Section 6.6)		✓		✓		✓		✓	✓		✓
DLCO (Section 6.4.4)	✓ ⁵										
6MWT (Section 6.4.5)	✓	✓							✓	✓	

⁴ Spirometry can be repeated once if acceptability and repeatability criteria as specified by ATS/ERS/JRS/ALAT are not met after confirmation by central reader.

⁵ [REDACTED]

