5.2.2. Pulmonary Function by Spirometry

Pulmonary function will be assessed through spirometry at the study center. All spirometry evaluations should be performed pre-bronchodilator*. Spirometry data taken post-bronchodilator will be excluded from the analysis. Values will be used as provided by the central reading vendor.

* pre-bronchodilator is defined as:

- short-acting more than (>) 6 hours prior to the spirometry assessment
- long-acting bronchodilator at least (\geq) 12 hours prior to the spirometry assessment

Note that a spirometry assessment with no use of bronchodilator is equivalent to a pre-bronchodilator assessment.

The data will be coded as “acceptable”, “borderline acceptable” and “unacceptable”.

“Unacceptable” values will be excluded from analyses. The following quality grades as provided in the database will be used.

Table 3 Spirometry Quality Grades Based on Acceptability and Repeatability criteria

Quality	Criteria
Acceptable	≥ 3 efforts that meet the American Thoracic Society / European Respiratory Society (ATS/ERS) Guidelines (Raghu, Collard, Egan, & al, 2011; Raghu, Remy-Jardin, Myers, Richeldi, & Ryerson, 2018) and the criteria for Acceptability and Repeatability
Borderline acceptable	≥ 2 efforts that meet the ATS/ERS Guidelines and the criteria for Acceptability and Repeatability, or ≥ 3 efforts that meet the ATS/ERS Guidelines and the criteria for Acceptability but not Repeatability
Unacceptable	≤ 1 effort that meets the ATS/ERS Guidelines and the criteria for Acceptability and Repeatability
Acceptability:	

- Time to Peak Expiratory Flow < 250 ms
 - Absence of artifact or cough
 - Exhalation \geq 6 seconds however demonstrated a 1 second plateau
 - Lack of technical problems during effort
- Repeatability:
- Will be based on the computer selected Best effort (highest) compared to next Best effort (second highest) based upon FVC values to be within 150 ml or within 100 ml when FVC \leq 1L

Source: Pulmonary Function Test (PFT) OverRead Guidelines for GLPG1205-CL-220

The following parameters will be presented as part of the spirometry assessment:

- FVC (mL)
- Percent predicted FVC (%)
- FEV₁ (mL)
- Percent predicted FEV₁ (%)
- FEV₁/FVC ratio
- FEF₂₅₋₇₅

Derived values:

- Change from baseline:
Change at time point t = (time point t value) – (baseline value)
- Percent change from baseline:
Percent change at time point t = 100 x (change at time point t) / (baseline value)

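### SAP 3.3.3 picks the Week 26 FVC by date and not by quality grade, so a non-repeatable Visit 9 session can be analysed while its acceptable later-day repeat is only listed

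*SAP*

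**What the plan says.** **Selection by date (SAP 3.3.3).** Windowing covers every record: "All assessments, including data collected on unscheduled visits, will be allocated to analysis windows based on the relative day of the assessment". The row for the primary time point gives target day, lower bound and upper bound as "Week 26 183 163 197". Within a window, "Per parameter and analysis window, the value closest to the target date will be used in analysis tables and figures", and "Other values will be listed only". For ties, "If more than one value is located at the same distance from the target day, then the latest in time will be selected"; values that remain tied are averaged.

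**Use of the quality grade (SAP 5.2.2 and Table 3).** Sessions are graded acceptable, borderline acceptable or unacceptable. Of the unacceptable ones the SAP says that these "values will be excluded from analyses. The following quality grades as provided in the database will be used". No order of preference is set between the other two grades. Borderline has two forms: at least two efforts that satisfy both sets of criteria, or at least three that satisfy acceptability but fail repeatability.

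**The repeat (Protocol 6.10, footnote 4).** Attached to the screening, baseline and Visit 9 spirometry: "Spirometry can be repeated once if acceptability and repeatability criteria as specified by ATS/ERS/JRS/ALAT are not met after confirmation by central reader". Protocol 6.1.1 also lists this repeat among the Visit 9/EOT and Visit 10/EOS procedures.

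**Baseline (SAP 3.3.3).** A separate rule applies: "For spirometry endpoints, the mean of the analysis values (detailed in Section 5.2.2 for spirometry) before the first dose of study medication" is used, with reduced variability as the stated reason.

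No visible text in either document says that a repeat replaces the session that prompted it.

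**The concern.** The repeat at Visit 9 is there to rescue a poor measurement at the time point that defines the primary endpoint. A session with three or more acceptable but non-repeatable efforts fails one of the criteria that prompt a repeat, yet it passes the only quality filter in the SAP. From then on it competes with its own repeat on calendar distance alone. The plan can thus collect a better FVC and then analyse the worse one. The primary analysis is an observed-case ANCOVA at each time point (SAP 5.2.2.1), so whichever value is selected enters the Week 26 comparison directly.

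**Working it through.** **Inputs**
- Week 26 target Day 183, window Days 163 to 197 (SAP 3.3.3, Table 2).
- Visit 9 regular window of 6 days either side (Protocol 6.1), that is Days 177 to 189.
- Repeatability limit of 150 mL between the best two efforts, or 100 mL when FVC is 1 L or less (SAP 5.2.2, Table 3).
- 40 and 20 evaluable subjects, 10% dropout, SD 200 mL, effects of 50 and 80 mL in a 50:50 mix (Protocol 7.1).

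**Step 1. The plan's own figures.** Mean effect = 0.5 × 50 + 0.5 × 80 = 65 mL. After dropout, 36 and 18 subjects remain. SE = 200 × √(1/36 + 1/18) = 57.74 mL. P(observed difference > 40 mL) = Φ((65 − 40)/57.74) = 0.6675, and P(> 20 mL) = Φ((65 − 20)/57.74) = 0.7821. The protocol's 67% and 78% reproduce. The point does not depend on them; they supply the scale for Step 4.

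**Step 2. The selection rule.** Let the first session be on day d and the repeat k days later, both in the Week 26 window. The first session is selected when |d − 183| < |d + k − 183|, which is the same as d > 183 − k/2.
- If d ≥ 183 and k ≥ 1, the repeat is always further away, so the first session is always selected. Example: borderline on Day 183, acceptable repeat on Day 185; Day 183 is analysed.
- If d < 183, the result depends on the gap. Example: Days 181 and 184 are 2 and 1 days from target, so the repeat is selected.
- If k = 0, the distances tie and the later value is selected, provided times are used. Without times the two would be averaged.

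**Step 3. How much of the visit window is affected.** Take d from 177 to 189 and a repeat 1 to 6 days later that also falls by Day 189:

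| Gap k (days) | Day pairs | First session selected |
|---|---|---|
| 1 | 12 | 6 |
| 2 | 11 | 5 |
| 3 | 10 | 5 |
| 4 | 9 | 4 |
| 5 | 8 | 4 |
| 6 | 7 | 3 |
| Total | 57 | 27 |

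With gaps of 1 to 7 days the count is 30 of 63. If the repeat may also fall after Day 189, it is 58 of 91. These are counts of calendar combinations, not probabilities.

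**Step 4. Scale of one affected subject.** Suppose, as an assumption, that one selected FVC is wrong by 150 mL. The arm mean moves by 150/18 = 8.3 mL (placebo) or 150/36 = 4.2 mL (GLPG1205). Against the SE of 57.74 mL these are 14% and 7%.

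**The case against.** **The trigger is inferred.** The protocol never names the borderline grade as the reason for a repeat, and one form of borderline meets both criteria. That stands. The point rests on the other form, where repeatability has failed, which on an ordinary reading is a criterion not met.

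**The matter may be settled elsewhere.** SAP 5.2.2 takes values as the central reading vendor provides them, and SAP section 1 refers technical derivations to a separate document. A precedence rule could sit in either place. If so, SAP 3.3.3 still states a different rule and needs reconciling.

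**Most repeats may be on the same day.** Protocol 6.1.1 lists the repeat as a Visit 9 step, and Protocol 6.4.1 prefers transmission during the visit. But transmission during the visit is required only for the first baseline session, and the repeat waits for central confirmation, so a later day is foreseeable.

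**Stronger readings that the documents do not support**
- *That about half of repeats would be lost.* The 27 of 57 count presupposes a borderline first session, a repeat on a different day, and equally likely day pairs. No repeat rate is given.
- *That the FVC is wrong by 150 mL.* That limit is the gap between two efforts in one session, not the error of the reported value, and it is not on the same scale as a between-group mean difference of 50 mL.
- *That the same fault affects baseline.* The date rule does not govern the spirometry baseline. All pre-dose analysis values are averaged on purpose and none is discarded.
- *That the result is biased.* Selection takes no account of treatment and conduct is blinded, so no direction is implied.

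**Conclusion.** The gap is real but small. As written, a Visit 9 session that failed repeatability can enter the primary analysis while its acceptable later-day repeat is only listed. This always happens when the first session is on or after Day 183 and the repeat is on a later day in the Week 26 window. It concerns borderline sessions only, since unacceptable ones are already excluded. The likely result is some avoidable measurement noise in a few subjects.

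The conclusion assumes that failed repeatability alone can prompt the repeat and that no unseen document gives the repeat precedence. In a non-confirmatory study (SAP 5.2.1) this does not threaten the conclusions, but the correction is cheap enough to make.

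**What to change.** Before unblinding, add to SAP 3.3.3, for spirometry:

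*Where a session at a visit was repeated because acceptability or repeatability criteria were not met, only the session with the better quality grade (the repeat if grades are equal) is eligible for that visit; the distance-to-target rule is then applied to the eligible values.*

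Keep the rule to repeats of the same visit. Grade precedence over the whole of Days 163 to 197 would do harm: a borderline early EOT value on Day 172 (11 days from target) could give way to an acceptable follow-up value on Day 196 (13 days from target), replacing an end-of-treatment measurement with one taken off treatment. Leave the baseline averaging rule unchanged.

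The cost is one sentence and a sort key on a grade already in the database, with no new data and no change to sample size or alpha. Programming must be able to tell which record repeats which. In a few subjects the selected value will lie a few days further from Day 183.

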3.4. Handling of Data

3.4.1. Handling of Missing Data

3.4.1.1. Handling of Missing Date-Time Data

No imputations will be done in case of missing date (time) fields, nor for the missing parts of partially known date (time) fields.

Assessments with missing date (time) will be omitted from the analysis.

Event-type data (e.g. adverse events, concomitant medications) with missing date (time) will be allocated to analysis periods using a worst-case approach as explained in the respective sections.

3.4.1.2. Handling of Missing Result Data

No imputation will be done of missing result data. That is, an observed cases (OC) analysis will be performed. Details on the sensitivity analyses to investigate the impact of missing data on efficacy parameters are described in Section 6.2.

3.4.1.3. Censoring of Time-to-Event Data

Subjects who do not report the event at the moment of the analysis, are censored at the date of last contact. The date of last contact is defined as the latest date collected in the CRF from the date of death, visit or assessment dates, AE dates, concomitant treatment dates, drug intake dates or lab test dates and trial completion date.

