4.2. OVERALL STUDY DESIGN

This study is a randomized, double-blind, parallel group, placebo-controlled, multicenter, Phase II study.

Approximately 60 eligible subjects with a centrally confirmed IPF diagnosis are planned to be randomized in a 2:1 ratio to GLPG1205 100 mg q.d. taken as 2 capsules, or matching placebo q.d. administered for 26 weeks on top of local standard of care. Standard of care is defined as receiving nintedanib, pirfenidone or neither nintedanib nor pirfenidone.

Individual dose reductions of GLPG1205 will be allowed once in case of intolerance or toxicity at the discretion of the investigator (Section 5.2). Subjects may have their dose of IMP reduced from 100 mg (2 capsules) q.d. to 50 mg (1 capsule) q.d. for the remainder of the study. Should the intolerance or toxicity continue, IMP may be discontinued, and the subject may be withdrawn from the study (refer to Section 4.3.5).

During the course of the study (post randomization) further adaptations of the treatment with nintedanib or pirfenidone due to e.g. intolerance or initiation of either nintedanib or pirfenidone is allowed based on the medical needs of the individual as judged by the investigator.

Enrolled subjects will come to the clinical study center at screening, Day 1 (baseline), Week 2, Week 4, Week 8, Week 12, Week 16, Week 20, Week 26, and, if applicable (i.e. for

early IMP discontinuation), the end of treatment visit (EOT). In addition, a follow-up visit will be planned 4 weeks after the last administration of IMP (i.e. Week 30/EoS). The end of the study is reached when the last follow-up visit as planned according the schedule of activities (Section 6.10) of the last subject is performed.

Subjects who stop IMP early need to be encouraged to complete the EOT and follow-up visit for safety assessments and pulmonary function, but will not be obliged to do so.

To enhance the safety of the subjects and integrity of the study data, an Independent Data Monitoring Committee (IDMC) will be implemented and clinical endpoint adjudication will be performed (see Section 8 for additional information).

For the in- and exclusion criteria please refer to Section 4.3.2, “[Inclusion Criteria](#)” and Section 4.3.3, “[Exclusion Criteria](#)”.

A schematic diagram of clinical study design is provided ([Figure 1](#)).

[figure not shown]

Figure 1 GLPG-1205-CL-220 Study Design

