4.3.5. Removal of Subjects from Therapy or Assessments

A subject may be withdrawn from the clinical study at any time without the subject's consent if the investigator or sponsor determines that it is not in the best interest of the subject to continue participation. In such case, the reason for withdrawal will be documented in the source documents, and the subject will be asked to complete the EOT visit and follow-up visit for safety assessments and pulmonary function.

Study treatment should be discontinued by the investigator (preferably after discussion with the CRO medical monitor, for any of the following conditions:

- Life-threatening AE or a SAE that places the subject at immediate risk
- Serious infections (those requiring parenteral antimicrobial therapy and/or hospitalization)
- Arrhythmia or conduction abnormality, including but not limited to prolonged QT interval corrected for the heart rate using Fridericia's formula (QTcF), where the severity is categorized as Common Terminology Criteria for Adverse Events (CTCAE) Version 5.0 Grade 3 or higher (i.e. QTcF \geq 501 ms or an increase from baseline (Visit 2) in QTcF of $>$ 60 ms) on at least 2 separate ECGs at the same visit
- Increase in liver function tests:
 - AST and/or ALT elevations $>$ 8x ULN: IMP treatment should be withheld and the LFTs should be repeated. IMP should be discontinued if the results are confirmed
 - AST and/or ALT elevations $>$ 3x ULN and $<$ 8xULN: IMP treatment should be withheld. If LFTs do not return to normal within 2 weeks then the IMP should be discontinued. If LFTs return to normal within 2 weeks then IMP could be restarted with close monitoring (e.g. repeat testing twice per week for the first 2 weeks then

weekly for the following month). In the event LFTs become abnormal at any subsequent point during the study (i.e. after rechallenge) then the IMP should be discontinued.

- AST and/or ALT elevations $>3x$ ULN and total bilirubin level (TBL) $>2x$ ULN or international normalized ratio (INR) >1.5 : IMP treatment should be withheld and the LFTs should be repeated. IMP should be discontinued if the results are confirmed.
- AST and/or ALT elevations $>3x$ ULN with the appearance of fatigue, nausea, vomiting, right upper quadrant pain or tenderness, fever, rash and/or eosinophilia ($>5\%$): IMP treatment should be withheld, LFT repeated and IMP discontinued if LFT confirmed or if symptoms and signs persist

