When IMP is discontinued, the subject will be requested to return for the EOT and EOS Visits to allow safety Follow-up.

Subjects will be informed prior to clinical study entry that they are allowed to withdraw from the clinical study. At any time and for any reason, a subject's participation in the clinical

study may terminate at his/her request without prejudice to his/her future medical care. The subject will be encouraged to share the reason(s) for withdrawal so this can be documented in the source documents, and to complete the EOT visit and follow-up visit for safety assessments and pulmonary function, but will not be obliged to do so.

Subjects who withdraw from the clinical study without contact with the site (lost to follow-up) should be contacted by the site so that their health status can be assessed and documented in the source documents. The site should make every effort to understand whether the subject is alive, including checking the medical records, contacting general practitioner or relatives, if necessary. All attempts (at least 3) must be documented in the source documents.

Subjects who drop out before the first administration of the IMP will be replaced. Subjects who stop taking IMP for any reason will not be replaced.

The sponsor has the right to terminate the clinical study at any time in case of safety concerns or if special circumstances concerning the IMP or the company itself occur, making further treatment of subjects impossible. In this event, the investigator(s) and relevant authorities will be informed of the reason for clinical study termination.

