7. PK blood sample (Visit 9: predose sample for GLPG1205, and if applicable postdose sample for nintedanib or pirfenidone concentration analyses; Visit 10/EOS: for GLPG1205, and if applicable also for nintedanib or pirfenidone concentration analyses)
8. Safety blood sampling for clinical laboratory evaluations (hematology, coagulation and clinical chemistry)
9. [REDACTED]
10. [REDACTED]
11. Safety urine sampling for clinical laboratory evaluations (urinalysis)
12. Dosing IMP on site (Visit 9)
13. [REDACTED]
14. 6MWT [REDACTED] (Visit 9/EOT)
15. [REDACTED]
16. Collect subject diary (Visit 9/EOT)
17. Collect returned IMP and review IMP compliance (Visit 9/EOT)
18. Repeat spirometry if acceptability and repeatability criteria as specified by ATS/ERS/JRS/ALAT are not met after confirmation by central spirometry reader

Addendum for Early treatment discontinuation Visit (EOT)**Alternative approach due to COVID-19 pandemic**

In case of an early treatment discontinuation, the following EOS visit, planned regularly 28 days after the last IMP intake, can occur either earlier by up to 7 days or later up to 28 days to enable the conduct of the EOS Visit on site (for more details see below in the Visit 10/EOS addendum). In addition:

- if the decision to discontinue the treatment was made during an on-site visit, and without any safety findings or ongoing AEs, the EOS Visit may be performed remotely.
- if the decision to discontinue the treatment was not made during an on-site visit, or in case of any safety observations or ongoing AEs, an EOS Visit on site is required to monitor the safety of the subject. In addition, remote or home unscheduled visits should be conducted at least every 14 days, until the on-site EOS Visit can be performed.

Addendum for Visit 9:**Alternative approach due to COVID-19 pandemic**

- If Visit 9 cannot be conducted on site according to the original schedule of activities (Section 6.10; see also Section 6.1, “[Timing of Assessments](#)”) due to the COVID-19 pandemic, the treatment period can be extended up to +56 days or shortened up to -28 days to enable the conduct of Visit 9 on site.
- If the study treatment is prolonged beyond the originally planned Visit 9 date, remote (e.g., telephone contact, virtual contact) or home unscheduled visits should be conducted at the originally planned visit date, and thereafter at least every 14 days, to closely monitor the patient’s safety until the on-site visit can be performed.

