6.5.1. Adverse Events

The AE reporting period for safety surveillance begins when the subject signs the ICF and ends at their last follow-up visit.

Detailed definitions, severity grades and reporting requirements for AEs and SAEs are found in Section 9.

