7.3.4.2. Secondary Efficacy Endpoints Analyses

The % predicted FVC change from baseline will be analyzed using a similar model as the one described for the primary analysis.

The proportions of subjects who have an absolute decline of 10 percentage points or more in % predicted FVC or who die will be analyzed using logistic regression.

Treatment effect on time to death (all cause and respiratory-related) / hospitalization (all cause and respiratory-related), whichever occurs first, will be assessed using the log-rank test. Kaplan-Meier estimates will be derived for probability of death (all cause and respiratory-related) / hospitalization (all cause and respiratory-related) (whichever occurs first) over time and displayed graphically.

SGRQ total score and domains will be analyzed using descriptive statistics of actual values and changes from baseline at all time points. The proportion of SGRQ responders (defined as absolute change from baseline at all time points, in SGRQ total score \leq -4 points) will also be tabulated.

SGRQ responders and proportion of subjects with hospitalization will be described and tested for treatment differences using a Fisher's exact test.

More detail will be provided in the SAP.

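### Death and hospitalisation are not followed to a common study date after an early IMP stop, so the major-event analyses rest on an untested censoring assumption

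*SAP*

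**What the plan says.** The endpoint is time from first dose to death or first hospitalisation (all-cause and respiratory-related), adjudicated blind (Protocol 4.1.2 and 8.2; SAP 5.2.3.1). It is analysed by log-rank test and Kaplan-Meier estimates. SAP 5.2.3.1 also reports the number and proportion of subjects with an event, and Protocol 7.3.4.2 adds Fisher's exact test on the proportion hospitalised.

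SAP 3.4.1.3 sets the censoring: "Subjects who do not report the event at the moment of the analysis, are censored at the date of last contact". Last contact is the latest of several CRF dates. How long a subject is observed follows from the protocol:

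- Section 4.2: "a follow-up visit will be planned 4 weeks after the last administration of IMP". That is Week 30 only for a completer. The early-discontinuation addendum in 6.1.1 agrees, describing EOS as "planned regularly 28 days after the last IMP intake".
- Section 4.3.5: "When IMP is discontinued, the subject will be requested to return for the EOT and EOS Visits to allow safety Follow-up". No other visit is requested, and 4.2 makes attendance encouraged rather than compulsory.
- Section 6.5.1: "The AE reporting period for safety surveillance begins when the subject signs the ICF and ends at their last follow-up visit". Section 9.3.2 extends SAE reporting to 30 days after the last dose. Beyond the follow-up period the site has no duty to look for SAEs, and reports one it hears of only if it is judged relevant to IMP.
- Section 4.3.5, for subjects lost to follow-up: "The site should make every effort to understand whether the subject is alive". No target date is given, and the result goes into the source documents.

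The sensitivity analyses in SAP 5.2.2.2 all concern FVC.

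**The concern.** Vital status and hospital admissions can be established without a visit, so they need not be lost when treatment ends. Under this plan, observation of an early stopper ends about four weeks after the last dose, while a completer is observed to about Week 30. A subject who stops early and attends EOS is even traced less than one who disappears.

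The reasons for stopping in Protocol 4.3.5 include worsening disease and serious or severe AEs. These may bear on prognosis, and AE-driven stops may differ between arms. Two problems follow. Kaplan-Meier and log-rank results are biased if the hazard after stopping differs from that of subjects still followed. Crude proportions are biased even if it does not, because under SAP 3.5.3 the denominator for event-type data is every subject in the analysis set and period, however briefly observed. At stake is the reading of a named secondary endpoint that has its own adjudication process.

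**Working it through.** **The plan's own figures.** The documents give no event rate, hazard ratio or power for this endpoint. Protocol 7.1 gives figures for FVC only. Mean difference = 0.5 × 50 + 0.5 × 80 = 65 mL. With 36 and 18 subjects after 10% dropout, SE = 200 × √(1/36 + 1/18) = 57.7 mL. The probabilities of observing more than 40 mL and more than 20 mL are then 66.75% and 78.2%, against the stated 67% and 78%. They reproduce, but bear on this point only through the 10% dropout figure.

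**Unobserved time.** SAP 3.3.3 puts Week 26 at Day 183 and Week 30 at Day 211, so a completer is followed for 210 days from Day 1. EOS = last dose + 28 days. Unobserved days = 211 - (last-dose day + 28).

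| Last dose | EOS | Unobserved days | Share of 210 |
|---|---|---|---|
| Day 29 (Week 4) | Day 57 | 154 | 73% |
| Day 57 (Week 8) | Day 85 | 126 | 60% |
| Day 113 (Week 16) | Day 141 | 70 | 33% |
| Day 141 (Week 20) | Day 169 | 42 | 20% |

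In weeks, a stop at week s loses 26 - s, so stops after Week 20 lose under 6. The COVID-19 windows shift this for individuals: an early stopper's EOS can be up to 28 days later, and a completer's end up to 56 + 28 = 84 days later.

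**Subject-time.** Assume the 10% dropout are all early IMP stoppers (6 of 60), with stop times uniform over Weeks 0 to 26. The mean loss is 13 weeks, and 6 × 13 = 78 of 60 × 30 = 1,800 subject-weeks (4.3%). At 20% and 30% stopping it is 156 (8.7%) and 234 (13%).

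**Missed first events and Kaplan-Meier bias.** Assume a constant hazard giving a 15% risk over 30 weeks: -ln(0.85)/30 = 0.0054 per week. With the hazard unchanged after stopping, at most about 0.0054 × 78 = 0.42 events are missed. Simulation, which allows for stoppers who would already have had an event, gives 0.38. The simulation multiplies the hazard by m after stopping, censors at stop + 4 weeks, and compares the Kaplan-Meier risk with the true 30-week risk. Cells show missed first events per 60 subjects, then bias in percentage points:

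| Stopping | m = 1 | m = 2 | m = 4 |
|---|---|---|---|
| 10% | 0.38; 0 | 0.71; -0.6 | 1.22; -1.4 |
| 20% | 0.74; 0 | 1.40; -1.1 | 2.46; -2.8 |
| 30% | 1.16; about 0 | 2.08; -1.5 | 3.70; -4.2 |

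With the assumed risk varied from 10% to 20%, 10% stopping gives 0.25 to 1.53 missed first events and bias of 0 to -1.8 points. The extreme of the range tried (20% risk, 30% stopping, m = 4) is -5.0 points.

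**Unequal stopping.** Take 30% stopping in one arm and 10% in the other, 15% risk, m = 4 and no other treatment effect. The true risk difference of 3.9 points appears as 1.2. With 20% against 10%, 2.0 appears as 0.5. At m = 1 Kaplan-Meier is unbiased, but the crude proportion is low by 1.16/60 = 1.9 points at 30% stopping and 0.38/60 = 0.6 points at 10%. The arm that stops more then looks about 1.3 points better only because it was watched for less time.

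**The case against.** The best defence is that this is a non-confirmatory proof-of-concept study, and that about 30 days after the last dose matches its treatment-emergent AE definition. With a half-life near 100 hours (Protocol 2.2.1), 28 days is 672/100 = 6.7 half-lives. That justifies a safety window. It does not make an endpoint described as time to major events an on-treatment one, and the plan does not label it so.

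Collection also does not simply stop. Lost subjects are traced for survival, later SAEs may be reported, date of death is among the CRF dates used for last contact, and Protocol 7.3.4.1 implies that some stoppers may complete visits to Week 26. All this stands, so it would be wrong to say that events are captured only through AE reporting. None of it is scheduled to a common date, however. The IDMC's look at adjudicated events (SAP 4.1) rests on the same incomplete follow-up.

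A reader might go further in four ways that the documents do not support:

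- *That the censored subjects are the highest-risk ones.* No hazard for stoppers is given. Those stopped because of a hospitalisation already have their composite event; for them only a later death is missed.
- *That any marked liver finding ends treatment.* Protocol 4.3.5 allows restart after some elevations and requires confirmation for others.
- *That one or two deaths would be missed.* No calculation supports this. The figures above are first events of either kind, and the 10% is FVC dropout, not an IMP-stop rate.
- *That a mortality test is distorted.* The log-rank test is on the first event. For all-cause mortality alone, SAP 5.2.3.1 clearly specifies only a frequency table of adjudicated categories. Protocol 7.3.4.2 also analyses subjects with an "absolute decline of 10 percentage points or more in % predicted FVC or who die will be analyzed using logistic regression", but this is absent from the visible SAP and SAP 5.2.4 is redacted, so its handling of deaths cannot be judged.

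**Conclusion.** The point holds in this limited form. No death or hospitalisation follow-up to a common date is scheduled after an early stop, event-free stoppers are censored at last contact, and no visible analysis tests whether that censoring is informative. The unobserved time follows directly from the schedule: large for early stops, small for late ones.

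The effect on results is uncertain and probably modest. At an assumed 10% stopping and 15% risk it is about 0.4 to 1.2 missed first events per 60 subjects and 0 to -1.4 points of Kaplan-Meier bias. It becomes larger only with more, or unequal, stopping combined with a raised hazard afterwards. Event risk, stop-time distribution and hazard multiplier are all assumptions. The documents do not show that GLPG1205 subjects will stop more often, so a hidden harm is a possibility rather than a finding. The change is worth making because it is cheap and protects the comparison whichever way stopping falls.

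**What to change.** In Protocol 4.3.5 and 6.10, for subjects who stop IMP early and have not withdrawn consent, add a telephone or medical-record check at the originally planned Week 26 and Week 30 dates. It should cover only vital status and hospitalisation (date and reason), be entered in the CRF, and send any event to the existing adjudicator. SAP 3.4.1.3 already takes the latest CRF date, so the check then counts as last contact without a separate censoring rule.

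If an amendment is no longer practical, describe the endpoint in SAP 5.2.3.1 as on-treatment plus about 30 days and add a sensitivity analysis for informative censoring.

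The cost is short amendment wording, a brief CRF entry, and one or two calls for a handful of subjects (about six if 10% stop). No site visit or procedure is added, and no treatment or stopping rule changes.
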